**Clinical Observation Of The Gynecological
Iron-Deficiency Anemia Treated With
Buxue Yimu Pills**

Version 2 (June,2017)

CONTENTS

A. OBJECT

B. STUDY METHOD AND DESIGN

C. TECHNICAL ROUTE

D. STATISTICS ANALYSIS

E. QUALITY CONTROL MEASUREMENT AND RESULT

PUBLICATION

F. SOURCE(S) OF FUNDING

A. OBJECT

Buxue Yimu Pills, Ferrous Sulfate each improve anemia, but they do so by different mechanisms. We generally treat patients with uncomplicated Iron Deficiency Anemia with oral iron due to the ease of administration, and Ferrous Sulfate is one of the most commonly used drugs.

Buxue Yimu Pills consists of multiple Chinese herbs including Angelica Sinensis, Astragalus, Donkey-Hide Gelatin, Herba Leonuri, Citrus etc., which gains widespread application in the treatment after women's abortion or operations of uterine cavity.

This study evaluates Buxue Yimu Pills, Ferrous Sulfate and the addition of Buxue Yimu Pills to Ferrous Sulfate in the treatment of Iron-Deficiency Anemia in adult women, with the object to perform clinical efficacy and safety assessment. In addition, we expect to conduct research on its pharmacodynamics, trying to probe into the mechanism and pharmacodynamic material basis of this mysterious traditional Chinese medicine.

B. STUDY DESIGN AND METHOD

— **STUDY DESIGN:** 180 women with mild to moderate Iron Deficiency Anemia were observed in a prospective multi-center randomized controlled clinical trial.

Inclusion Criteria:

1. Subject is a female between the age of 18 and 50.
2. Subject suffers from mild to moderate anemia with a hemoglobin between 80g/L and 110 g/L.
3. Subject has definite gynecological etiological factors of iron deficiency
4. Subject provides written informed consent.

Exclusion Criteria:

1. Subject underwent chronic digestive tract inflammation, uncontrolled digestive or urinary system bleeding.
2. Subject has other complications in addition to gynecological diseases leading to iron deficiency, such as hemorrhagic diseases of hematologic system, parasitic diseases like ancylostomiasis, chronic intravascular hemolysis, mechanical hemolysis like prosthetic valve, renal dysfunction and hemodialysis.
3. Subject is pregnant or lactating.
4. Subject has a severe systemic disease, such as cardiovascular system
5. Subject has a history of malignancy or radiotherapy.
6. Subject has undergone any Iron deficiency anemia treatment including Iron supplements or blood transfusion within 1 month prior to randomization.
7. Subject has mental disorder incapable of elementary cooperations.
8. Subject has participated in other clinical researches of medicine within 1 month prior to randomization.

—**METHODS:** The participants were divided randomly into 3 groups:

- a. Experimental group1(60 patients): Buxue Yimu Pills 12g pill by mouth, twice daily.
- b. Experimental group2(60 patients): Buxue Yimu Pills 12g pill by mouth, twice daily and Ferrous Sulfate 0.3g tablet by mouth, three times daily.
- c. Active Comparator group (60 patients): Ferrous Sulfate 0.3g tablet by mouth, three times daily.

—**TREATMENT PERIOD:** 1month.

—**OUTCOMES MEASUREMENT :**

Primary Outcome (Anemia Related Assessment, Clinical Efficacy Assessment): Complete Blood Count, Urine Routine, Reticulocyte Count, Iron Metabolism index (Serum Iron, Total Iron Binding Capacity, Serum Ferritin), Coagulation Indexes (Activated Partial Thromboplastin Time, APTT), Prothrombin Time (PT), Fibrinogen (FIB), Thrombin Time(TT), The Short Form-36 Health Survey (Sf-36).

Secondary Outcome (Safety Assessment): Hepatic Function, Renal Function, Blood Glucose, Electrolyte Semiconductor Junction, Electrocardiogram(ECG)

Other Pre-Specified Outcome (Metabonomics Assessment): Build up a new therapeutic evaluation system about Buxue Yimu Pills in the treatment of Gynecological Iron-Deficiency Anemia, which integrating clinical information with metabonomics, to probe into the mechanism and pharmacodynamic material basis of this mysterious traditional Chinese medicine.

C. TECHNICAL ROUTE

Screening Period (Day -30~0)

1. We enrolled in-patients according to the uniform inclusion/ exclusion criteria above, and informed consent will be signed by all study participants before joining in the study.
2. Collect medical history and certain demographic features of every participant, and perform general physical examination as well as gynecologic physical examination.
3. Complete outcomes measurement above.
4. Make the appointment for the follow-up.

The First Follow-Up Period (Day -30~0)

1. Group randomly and distribute medicine and patient diary pamphlet.
2. Inform application notice.
3. Make the appointment for the next follow-up.

The Second Follow-Up Period(Day0~30)

1. Collect medical history and certain demographic features of every participant, and perform general physical examination as well as gynecologic physical examination, again.
2. Complete outcomes re-measurement above.
3. Take back the medicine and patient diary pamphlet.

D. STATISTICS ANALYSIS

Data was analyzed using SPSS Version 18. All quantitative informations are expressed as mean values \pm standard deviation (SD). Statistical significance was assessed using unpaired Student's t-test or chi-square test. Probability values of less than 0.05 were considered significant and an asterisk identifies such significance in the figures. We will also compare the adverse effect of each group using descriptive statistics.

E. QUALITY CONTROL MEASUREMENT AND RESULT PUBLICATION

1. Every center of the research possesses the competence of scientific research to conduct clinical studies. Special people from each center will be put in charge of the research and monitoring the whole procedure. The rights and interests, responsibility and obligation of all centers will be standardized with the research agreement.
2. The maintenance, secrecy and safety of data and informations will be guaranteed by Department of Obstetrics and Gynecology, Peking Union Medical College Hospital.
3. Every center is responsible to subject enrollment and finish the prospective follow up.
4. The researchers' findings will be released in a paper published online.

F. SOURCE(S) OF FUNDING

1. This study does not charge any fee to any patients.
2. All the investigational drugs and cost of the study are provided by Qian Jin Pharmaceutical CO., LTD.

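### No balancing on center or gynecological cause is specified, and the unpaired t-test uses neither these nor the baseline values, so precision is given up to the extent that they predict outcome

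*Combined protocol and SAP*

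**What the plan says.** The Study Design paragraph of section B describes a "prospective multi-center randomized controlled clinical trial" in 180 women. Inclusion criterion 3 reads "Subject has definite gynecological etiological factors of iron deficiency". It lists no causes and sets no categories.

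Allocation is described twice. Methods in section B says "The participants were divided randomly into 3 groups", each of 60. The first follow-up step of section C says "Group randomly and distribute medicine and patient diary pamphlet". Neither gives a sequence method, blocks, strata or minimization.

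At screening, section C has staff "Collect medical history and certain demographic features of every participant, and perform general physical examination as well as gynecologic physical examination", and then take all the outcome measurements, which are repeated at the second follow-up. Baseline values therefore exist for every outcome. Cause is not named as a data item.

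Section D says "Statistical significance was assessed using unpaired" Student's t-test or a chi-square test. No covariate, center term or baseline value enters the analysis.

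**The concern.** Three pieces of pre-randomization information could predict the one-month result: the baseline value of the outcome, the center, and the reason for the iron deficiency. On cause, it is plausible that a woman whose bleeding continues and a woman whose blood loss was a single event reach different hemoglobin values at one month even from the same start. That is clinical reasoning; the documents give no figure for it.

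If such factors do predict outcome, a two-sample t-test leaves their variance in the error term, and when the arms differ on them by chance it makes no correction. The plan gives no effect size, SD or power for 60 per arm, so there is no documented margin to absorb lost precision.

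**Working it through.** **Inputs from the documents.** Three arms of 60 (3 x 60 = 180, which agrees with the stated total); significance at 0.05, taken as two-sided; unpaired t-test; treatment period of one month. The sample size itself cannot be reproduced, because no effect size, SD or power is stated.

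**Assumptions.** A binary cause with prevalence p of 0.3 to 0.5, whose two groups differ in day-30 outcome by d within-group SDs, with d from 0.2 to 1.0. Simple randomization.

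**Step 1: share of variance explained by cause.** R² = p(1-p)d² / [1 + p(1-p)d²]. For example, at p = 0.5 and d = 1.0, p(1-p)d² = 0.25 and R² = 0.25/1.25 = 0.20.

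**Step 2: power.** With 60 per arm and error SD equal to the within-group SD, the non-central t distribution gives 80% power for 0.516 SD. Without adjustment that effect shrinks, in units of the larger SD, to 0.516 x √(1-R²). At R² = 0.20 this is 0.516 x 0.894 = 0.461.

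**Step 3: equivalent sample size.** Adjusting at 60 per arm gives the precision of 60/(1-R²) unadjusted, a gain of 60 x p(1-p)d² per arm.

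| d | p | R² | t-test power (80% if adjusted) | Gain, women per arm |
|---|---|---|---|---|
| 0.2 | 0.3 | 0.008 | 79.7% | 0.5 |
| 0.3 | 0.5 | 0.022 | 79.1% | 1.4 |
| 0.5 | 0.3 | 0.050 | 78.0% | 3.2 |
| 0.5 | 0.5 | 0.059 | 77.6% | 3.8 |
| 1.0 | 0.3 | 0.174 | 72.1% | 12.6 |
| 1.0 | 0.5 | 0.200 | 70.7% | 15.0 |

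**Step 4: chance imbalance.** Ten points is 6 women in 60, and 15 points is 9. From two independent Binomial(60, p) counts, a given pair of arms differs by at least 10 points in 27% (p = 0.3) to 32% (p = 0.5) of trials, and by at least 15 points in 9% to 12%. For at least one of the three pairs the figures are 52-57% and 21-27%.

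**Step 5: what an imbalance does.** The shift is the imbalance times d. At 15 points and d = 0.5 to 1.0 it is 0.075 to 0.15 SD. Against a standard error of √(2/60) = 0.183 SD, that is 0.41 to 0.82 standard errors.

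**Step 6: error rates** (simulation, 40,000 trials per setting, p = 0.5). Over all randomizations the t-test's type I error stays at 4.9-5.1% for every R² tried from 0 to 0.30. Among trials with an imbalance of at least 15 points it is 7.0% at R² = 0.05 and 11.5% at R² = 0.20, while the adjusted model stays near 5%. If the arms are stratified on cause but the t-test is kept, type I error falls to 4.5% and 2.8% at the same R² values, so stratification factors also belong in the analysis. With R² = 0, adjusting costs almost nothing: simulated power for a 0.5 SD effect is 77.3% with the t-test and 77.0% adjusted.

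**The case against.** The strongest reply is that the prognostic strength of cause is unknown. The split between a single bleeding event and continuing loss is not in the protocol, and section A's remark about use after abortion or uterine-cavity operations describes where the product is used, not who will enter this trial. With a weak predictor there is almost nothing to gain. This stands, and it is why the loss is stated as a range that starts near zero.

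The power figures also compare adjustment for cause alone with no adjustment. What cause adds once baseline is in the model could be smaller, and no figure for center or baseline can be derived because the documents give no correlations. This stands too.

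A reader might infer more than the text supports on three points:

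- That cause is already recorded as a variable. It is only an eligibility condition; history and examination are collected, but no coded field is named.
- That randomization is known to be unbalanced on cause or center. The method is not stated, so one can say only that no balancing is specified.
- That the results would be biased or the 5% level inflated. Step 6 shows that the overall error rate holds; the excess error arises only conditionally, in trials that happen to be imbalanced.

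Finally, section B names a battery of primary outcomes, not one, so an assumption made for hemoglobin need not hold for the rest. That limits how far the figures carry. It does not remove the case for using baseline and center.

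**Conclusion.** The point holds as a conditional loss of efficiency. The plan specifies no balancing on center or cause, and its t-test uses neither of them nor the baseline values. The estimate is unbiased on average and the overall error rate stays at 5%.

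For cause alone, the cost runs from under 1 power point (R² of 1-2%) to between 2 and 9 points (R² of 5-20%), on the assumptions of a binary cause at 30-50% prevalence and a continuous outcome. The imbalance figures also assume simple randomization, and for any one comparison the 27-32% and 9-12% figures are the relevant ones. An unconditional claim that precision is being lost would go beyond the documents. The change is still worth making, because it is nearly free even if the factors turn out not to matter.

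**What to change.** In section D, for each continuous efficacy outcome (hemoglobin first), replace the unpaired t-test with a linear model containing arm, the baseline value of that outcome and center. Merge small centers by a rule set in advance.

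State the randomization method. Where it is still possible, record cause in two or three fixed levels before randomization, stratify the allocation by center and cause, and include cause in the model.

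If enrolment has started, adjust for baseline and center. Add cause only if it is coded from pre-randomization screening records by staff unaware of allocation; the documents describe no blinding, so cause classified later with the arm known could itself introduce bias.

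The cost is one extra coded screening item, possible pooling of sparse center-by-cause cells, and a revised paragraph in section D. No additional patients or visits are needed.

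### No entry criterion uses the liver result taken at screening, and no baseline-adjusted liver analysis is stated, so pre-existing liver abnormality can enter the trial and add noise to its first-listed safety outcome

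*Combined protocol and SAP*

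**What the plan says.** **Eligibility (section B).** None of the four inclusion and eight exclusion criteria mentions liver disease, hepatitis or a liver-test limit. Exclusion 2 opens with "Subject has other complications in addition to gynecological diseases leading to iron deficiency" and gives examples that end with "chronic intravascular hemolysis, mechanical hemolysis like prosthetic valve, renal dysfunction and hemodialysis". The nearest criterion that could reach the liver is exclusion 4: "Subject has a severe systemic disease, such as cardiovascular system". It requires severity and contains no laboratory limit.

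**Outcomes (section B).** The safety list begins "Secondary Outcome (Safety Assessment): Hepatic Function, Renal Function, Blood Glucose".

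**Schedule (section C).** Screening item 3 is "Complete outcomes measurement above", which takes in hepatic function. Grouping and dispensing follow at the First Follow-Up. The next scheduled liver test is at the Second Follow-Up: "Complete outcomes re-measurement above". No sentence says who reviews the screening result or what follows from an abnormal one.

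**Analysis (section D).** "Statistical significance was assessed using unpaired Student's t-test or chi-square test", and "Probability values of less than 0.05 were considered significant". The section does not say whether final values or changes are tested. It names no baseline covariate and does not define a liver abnormality that is new on treatment.

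**The concern.** Safety is part of the stated object of the study, and the liver result leads the safety list. The liver test is taken before grouping, but the protocol makes no use of the result there. Two things are at stake.

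- **Exposure.** A woman with abnormal but not severe liver tests may receive the herbal product, iron or both for a month, with no protocol step that looks at her result first. No later analysis can repair this.
- **Readability of the liver comparison.** If final values go straight into an unpaired test, a few women with long-standing high values widen the standard deviation. With 60 per arm they may also fall unevenly between arms. A real drug-related shift then becomes harder to see.

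**Working it through.** **1. Text check.** Reading all twelve criteria for a liver term or a laboratory limit on the liver finds none. Severe liver disease can reasonably be read into exclusion 4, so the gap concerns mild to moderate abnormality.

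**2. Plan's own figures.** The plan gives no liver effect size, variance, prevalence or power to reproduce. From the documents: 3 × 60 = 180 women and a 0.05 significance level, taken here as two-sided because sidedness is not stated.

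**3. Assumptions (not in the documents).** ALT 20 ± 8 U/L in unaffected women; a share q of 2% to 5% with values near 100 U/L that persist to the final visit; a true between-arm shift of 5 U/L.

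**4. How many women, and how uneven.**
- Expected number: 180 × 0.02 = 3.6 and 180 × 0.05 = 9.
- With independent Binomial(60, q) counts, the chance that two given arms differ by two or more such women is 30% at q = 2% and 52% at q = 5%.
- Each affected woman moves her arm's mean by (100 − 20)/60 = 1.33 U/L. An imbalance of two moves the difference by 2.67 U/L, about half of the 5 U/L sought.

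**5. Unpaired t-test on final values.** Variance = 8² + q(1 − q) × 80²; SE = SD × √(2/60).

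| q | SD | SE | 5/SE | Power, formula | Power, simulated |
|---|---|---|---|---|---|
| 0 | 8.0 | 1.46 | 3.42 | 92% | 92% to 93% |
| 2% | √(64 + 125.4) = 13.8 | 2.51 | 1.99 | 50% | about 54% |
| 5% | √(64 + 304) = 19.2 | 3.50 | 1.43 | 29% | about 32% |

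The simulation (40,000 trials per row, each woman affected at random with probability q) is preferred because the mixture is skewed and the formula treats it as normal.

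**6. Change from baseline, same women.** The persistent 80 U/L excess cancels. The change has variance 2(1 − r) × 8², where r is the correlation of baseline and final values within affected and within unaffected women.
- r = 0.5: SD 8.0, simulated power about 92% at both 2% and 5%.
- r = 0.3: SD 9.5, power 82%. r = 0.7: SD 6.2, power 99%.
- With the screening value as covariate and r = 0.5, power is 95% at 2% and 93% at 5%.
- If affected women's values vary with SD 20 to 30 instead of 8 (r = 0.5), change from baseline gives 90% to 86% at 2% and 86% to 76% at 5%. That is less than full recovery, but far above the final-value test.

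**7. Chi-square test.** Assume new abnormality in 1% versus 15%, added to a pre-existing share q: p₁ = q + (1 − q) × 0.01 and p₂ = q + (1 − q) × 0.15. The normal-approximation power at 60 per arm is about 81% at q = 0, 72% at 2% (3.0% versus 16.7%) and 60% at 5% (6.0% versus 19.3%). Counts this small make the approximation rough.

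**8. False-positive check.** With no true difference, the final-value t-test rejects in 4.4% of simulated trials at q = 2% and 4.6% at q = 5%. One woman at 100 U/L in one arm gives about 4%, and one at 200 U/L about 0.8%. None exceeds 5%.

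**The case against.** The strongest defence is that the statistical harm comes from the analysis and not from eligibility. Randomization leaves no systematic bias, a baseline value is already collected, and section D does not actually say that raw final values are tested. Adjusting for baseline would remove most of the noise without excluding anyone. This stands, and it is why the fix includes the analysis. It does not answer the exposure point.

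It can also be said that severe liver disease falls under exclusion 4, and that history and physical examination precede grouping. Both are true; they confine the gap to mild to moderate abnormality and to results visible only in the laboratory. All liver inputs above are assumptions, which also stands: they show a range and do not estimate this trial.

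Three stronger readings are tempting, and the documents do not support them.

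- *A reader might infer that the protocol protects the kidney and forgot the liver.* Renal dysfunction appears in exclusion 2 as a competing cause of iron deficiency, not as an organ-safety screen, so its presence does not make the absence of the liver an inconsistency.
- *A reader might infer that such women could create a false liver signal.* Step 8 shows that the false-positive rate does not rise.
- *A reader might infer that one outlying woman cuts power to some fixed figure.* It depends on her arm. At 100 U/L, power is about 43% if she is in the lower arm and 95% if she is in the higher one.

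**Conclusion.** The concern holds in a limited form. As written, women with mild to moderate pre-existing liver abnormality are eligible, and nothing requires the screening result to be looked at before they are grouped and given drug. If final values are compared, they add noise and chance imbalance to the first-listed safety outcome. Under the stated assumptions, roughly two-fifths of the power is lost at 2% prevalence (92% to 54%) and about two-thirds at 5% (92% to 32%); most or all of it is recoverable from the baseline value already taken. The true size is unknown, because the documents give no prevalence, liver values or target difference. This concerns a secondary safety outcome and leaves the efficacy comparison untouched. It should be corrected, but it does not threaten the trial's main result.

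**What to change.** 1. **Entry.** Add a hepatic function criterion to the exclusion criteria in section B, with its limit set by the sponsor's clinical team. In section C, require that the screening liver result be reviewed before grouping and dispensing.
2. **Analysis.** In section D, state that liver tests are analysed as change from the screening value, or with that value as covariate, and that only abnormalities new after the start of treatment are counted, with the definition written down in advance.

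**Cost.** A few protocol sentences and no new test or visit. On the assumed 2% to 5%, a few screened women would be replaced, and the results would apply slightly less widely, since they would not cover women outside the chosen limit. The second item costs nothing in recruitment and is worth making even if the clinical team sets a permissive limit.

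### Eleven measures share the primary outcome in a three-arm trial with no lead measure, declared contrast, success rule or multiplicity control; if any one may count, the false-positive chance against iron is about 23% to 65%

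*Combined protocol and SAP*

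**What the plan says.** Section B (outcomes measurement) opens its list with "Primary Outcome (Anemia Related Assessment, Clinical Efficacy Assessment): Complete Blood Count, Urine Routine, Reticulocyte Count, Iron Metabolism index". The iron group is spelled out as "Iron Metabolism index (Serum Iron, Total Iron Binding Capacity, Serum Ferritin", and after APTT the list closes with "Prothrombin Time (PT), Fibrinogen (FIB), Thrombin Time(TT), The Short Form-36 Health Survey (Sf-36". Separate safety tests follow under "Secondary Outcome (Safety Assessment): Hepatic Function, Renal Function, Blood Glucose", so the clotting and urine tests have been placed among the primary efficacy measures, not with safety.

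Section B (methods) randomizes 60 women to each of three arms: the pills alone, the pills plus Ferrous Sulfate, and Ferrous Sulfate alone. The last is labelled "Active Comparator group (60 patients"). Section A says the study evaluates all three and starts from the premise that "Buxue Yimu Pills, Ferrous Sulfate each improve anemia, but they do so by different mechanisms". It does not say whether the pills alone are meant to beat iron or to be no worse than it.

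Section C gives the timing of the final assessment only as "The Second Follow-Up Period(Day0~30") with the instruction "Complete outcomes re-measurement above".

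Section D names two-sample t-tests and chi-square tests, calls any P value below 0.05 significant, and marks it with an asterisk in the figures. It names no primary comparison, order of testing, rule for success or adjustment.

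**The concern.** A primary outcome should settle in advance which result decides the question. Here no measure leads, and three of the entries (blood count, urine routine, SF-36) each yield several results. A t-test compares two groups, so three arms imply pairwise testing, but the pairs are not declared. The only decision rule is a per-test threshold.

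Two consequences follow. First, no pattern of results is defined as success or failure. Second, if one significant primary measure may be reported as a positive primary result, 0.05 is not the trial's error rate. A chance finding on an anemia measure would directly support a claim of benefit. A chance finding on APTT or urine routine would not support that claim, but would still be labelled a significant primary result.

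**Working it through.** The documents give no trial-level error rate, power, effect size or standard deviation. The only design figure that can be reproduced is 3 × 60 = 180.

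**Inputs from the documents**
- Number of primary measures (Section B): blood count, urine routine, reticulocytes, serum iron, TIBC and ferritin make 6; APTT, PT, FIB, TT and SF-36 make 5; total 11. If the iron and clotting groups each count once, 11 − 2 − 3 = 6.
- Anemia laboratory measures: blood count, reticulocytes, serum iron, TIBC and ferritin, so 5.
- Arms: three, 60 each (Section B).
- Threshold: 0.05 per test (Section D).

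**Assumptions, since the documents are silent**
- Any one significant primary measure may count.
- Two-sided t-tests, one test per measure per pair. This favors the plan, because three of the entries hold several results.
- Normal measures with a common correlation between 0 and 0.9.
- No true difference on the measures counted.

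**One pair, uncorrelated measures.** Chance of at least one false positive = 1 − 0.95^K:
- K = 11: 1 − 0.95^11 = 0.431
- K = 6: 1 − 0.95^6 = 0.265
- K = 5: 1 − 0.95^5 = 0.226

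**Two contrasts against Ferrous Sulfate.** They share the iron arm, so on any one measure the two mean differences have correlation (σ²/60)/(2σ²/60) = 0.5. Treating all 22 tests as independent would give 1 − 0.95^22 = 0.676, slightly too high. Simulation (50,000 trials per setting, n = 60 per arm, pooled t-tests) allows for the sharing:

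| Correlation among measures | 0 | 0.3 | 0.5 | 0.7 | 0.9 |
|---|---|---|---|---|---|
| 11 measures | 64.7% | 58.2% | 49.2% | 37.7% | 22.8% |
| 6 measures | 43.5% | 39.8% | 35.1% | 28.4% | 19.1% |
| 5 anemia measures | 37.8% | 35.4% | 31.4% | 25.8% | 17.9% |

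The 6-measure row also covers the case in which the five anemia measures truly differ and the other six do not. A separate run of 1,000,000 replicates gave 64.9%, 48.7% and 22.7% for 11 measures at correlations 0, 0.5 and 0.9.

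**Other numbers of pairs (correlation 0 to 0.9)**

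| | One pair | All three pairs |
|---|---|---|
| 11 measures | 43% to 13% | 76% to 29% |
| 6 measures | 27% to 11% | 54% to 25% |
| 5 anemia measures | 23% to 10% | 48% to 23% |

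The most lenient setting in these tables is about twice 5%.

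**One endpoint, two contrasts (400,000 trials):** 9.1% unadjusted, 4.7% with Holm.

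**The case against.** The strongest reply is that the headline range depends on a rule the plan does not contain. Section D puts an asterisk on a small P value; it does not say that an asterisk means efficacy, and it never claims a 5% rate for the trial as a whole. This stands as a condition on the figures. If every measure had to be significant, there would be no inflation across measures. But the plan supports that reading no better than the other, and leaving the rule open is itself the defect.

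Five of the eleven measures (urine routine and four clotting tests) would not support an anemia claim. This stands too: for such a claim, 18% to 38% is the more relevant range. It is still well above 5%.

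The correlation is assumed, and 0.9 across blood, urine, clotting and questionnaire results is implausibly high. With correlation only within the five anemia measures and within the four clotting tests (0.5 to 0.9 within, 0 between), the chance is 58% to 43%. Nor is 23% a floor: a common correlation of 0.95 gives 18.1%, and fewer truly null measures would also lower it. Even at correlation 1, two unadjusted contrasts leave 9%. The chi-square tests were not modelled.

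Finally, the arm labels do imply two contrasts against iron. They imply them; they do not declare them primary.

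**Conclusion.** The concern holds and must be fixed. The plan has no lead measure, declared primary contrast, success rule or multiplicity control, and nothing elsewhere in the document supplies them. That conclusion needs no simulation.

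The size is conditional. If any one significant measure may count, two contrasts against iron carry a false-positive chance of about 23% to 65% for eleven null measures, 19% to 43% for six, and 18% to 38% for the five anemia laboratory measures alone. These figures assume two-sided tests, 60 per arm and a common correlation of 0.9 down to 0. As written, the trial cannot give a confirmatory answer on the pills, alone or added to iron.

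**What to change.** Before outcome data are examined:

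1. Name one primary endpoint. Hemoglobin at the end of the one-month treatment period is recommended: it is already in the blood count and it defines eligibility. The sponsor may justify another single measure. State the visit day and window, and the form of analysis, for example the final value adjusted for the screening value.
2. Declare two primary contrasts against Ferrous Sulfate: the combination, and the pills alone. State that each is a two-sided test of difference, and hold their joint error at 0.05 by Holm or a justified fixed order.
3. Move the other listed measures to secondary or safety outcomes, reported as estimates with 95% confidence intervals and without confirmatory significance claims.
4. Also advisable: state that, with no placebo or untreated arm, a non-significant result for the pills alone shows neither benefit nor equivalence to iron. A claim of being no worse than iron needs a pre-specified non-inferiority test with a justified margin.

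**Cost.** Items 1 to 3 need no new patients or measurements, but fewer results can be called significant. At 60 per arm and 80% power, before dropout, the detectable difference rises from 0.52 SD (two-sided 0.05) to 0.57 SD (two-sided 0.025, the first Holm step). Baseline adjustment would recover some of this: at an assumed correlation of 0.5 with the screening value, 0.516 × √(1 − 0.25) = 0.45 SD.

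For the pills alone, the unadjusted 95% confidence interval extends 1.980 × √(2/60) = 0.36 SD either side of the estimate. A non-inferiority test with truly equal arms has 80% power only for a margin of (1.960 + 0.842) × √(2/60) = 0.51 SD at one-sided 0.025, or 0.56 SD at one-sided 0.0125 (normal approximation; exact t calculations give 0.52 and 0.57). That claim may therefore need more patients.

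Section D mixes past and future tense, so the trial's status is unclear. If outcome data have already been seen, the change cannot restore error control: the choice should be labelled post hoc and the results exploratory.

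### Four clotting tests are primary outcomes under an unadjusted t-test, but use of drugs that act on clotting is neither an eligibility criterion nor a specified data item

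*Combined protocol and SAP*

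**What the plan says.** Section B, Outcomes Measurement, lists as primary, among blood count, iron indices and SF-36, the "Coagulation Indexes (Activated Partial Thromboplastin Time, APTT), Prothrombin Time (PT), Fibrinogen (FIB), Thrombin Time(TT"). Section C has every outcome measured at screening and again at the second follow-up, after one month of treatment.

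Eligibility requires that the "Subject has definite gynecological etiological factors of iron deficiency". Exclusion 2 removes other causes of deficiency, "such as hemorrhagic diseases of hematologic system, parasitic diseases like ancylostomiasis, chronic intravascular hemolysis, mechanical hemolysis like prosthetic valve". Exclusion 4 removes severe systemic disease, with the cardiovascular system as its example. Exclusion 6 concerns anemia treatment in the preceding month, and exclusion 8 concerns other drug trials. No criterion names an anticoagulant, antiplatelet or hemostatic drug. There is no concomitant-medication section and no list of prohibited drugs.

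Section C takes a medical history at both visits, and a patient diary is handed out and collected. The contents of neither are described.

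Section D states: "Statistical significance was assessed using unpaired Student's t-test or chi-square test", and "Probability values of less than 0.05 were considered significant". It gives no baseline adjustment, rank-based method, rule for extreme values or sensitivity analysis.

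**The concern.** A gynecological cause of iron deficiency will often mean bleeding. That is an inference, since the criteria do not use the word, but a natural one. Such women may be taking a drug that affects clotting, or may be given one for the bleeding during the treatment month. Exclusions 2 and 4 remove some likely users through their condition, none through the drug.

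A t-test on raw means is sensitive to extreme values. A user admitted under the criteria can inflate the SD enough to hide a true difference. Drugs started after randomization are a further problem: their use can differ by arm, randomization does not protect against that, and the plan specifies no data item that would reveal it. A starred clotting difference, or its absence, could then not be interpreted. Drug use that was never recorded may not be recoverable at analysis.

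**Working it through.** **Inputs from the documents.** Section B gives 180 women, 60 in each of three arms ("Active Comparator group (60 patients"); 3 × 60 = 180 agrees. No effect size, SD or power is given behind that number, so there is no sample-size calculation to reproduce. Section D gives the unpaired t-test and the 0.05 threshold. Two-sided testing is assumed, since sidedness is not stated.

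**Assumed inputs.** The documents give no clotting values. I take PT 12.0 ± 0.8 s, a true between-arm shift of 0.5 s, and a user's PT anywhere from 15 to 30 s. Let k be her distance from 12.0 s in SDs, k = (PT − 12.0)/0.8.

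**1. No user.** SE = 0.8 × √(2/60) = 0.146 s. The critical t on 118 df is 1.98, so significance needs an observed difference of 1.98 × 0.146 = 0.289 s. Power ≈ Φ((0.5 − 0.289)/0.146) = Φ(1.44), or 92–93%.

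**2. One user in each arm, equal values.** The mean shifts cancel, but each arm's SD becomes about 0.8 × √(1 + k²/60). The estimated SE grows with it. The true trial-to-trial variation of the difference stays near 0.146, because her value is a fixed extreme and not sampling noise. So power ≈ Φ((0.5 − 1.98 × SE)/0.146). The last column is from simulated trials.

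| User's PT (s) | k | SD (s) | SE (s) | 1.98 × SE | Power, formula | Power, simulated |
|---|---|---|---|---|---|---|
| 15 | 3.75 | 0.89 | 0.162 | 0.321 | 89% | 89% |
| 18 | 7.5 | 1.11 | 0.203 | 0.403 | 75% | 76% |
| 20 | 10 | 1.31 | 0.239 | 0.472 | 58% | 59% |
| 25 | 16.25 | 1.86 | 0.339 | 0.672 | 12% | 12% |
| 30 | 22.5 | 2.46 | 0.449 | 0.889 | 0.4% | 0.4% |

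**3. One user in one arm only.** The answer depends on the arm. If she is in the longer-PT arm, simulated power is about 95% (PT 20 s), 92% (25 s) and 84% (30 s). If she is in the shorter-PT arm, it is about 44%, 5% and 0.1%.

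**4. False positives, no true effect, one user in one arm.** Her expected t is (k/60)/√((2 + k²/60)/60). This is 0.67 at k = 10 and 0.88 at k = 20, and it tends to 1.0 (p about 0.32) however extreme she is, because she inflates the SD along with the mean. Simulated false-positive rates are about 5% at PT 15 s, falling to 0.7% at 30 s.

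**5. False positives, several users in one arm.** Three users give about 11–19% across PT 15–30 s. Six give about 45% at 16 s and over 99% at 30 s.

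**The case against.** Most of the case on the other side stands.

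- A reader might infer that one treated woman could by herself produce a significant clotting result. Step 4 shows she cannot: she can tip a comparison only if it is already near significance, at best one with t about 1.71 (p = 0.09) without her.
- A reader might put the inflated SD into a standard power formula for one user in one arm and get about 32% at PT 30 s. That treats her fixed value as sampling noise and ignores her arm. Step 3 gives 84% or 0.1%.
- At PT 15 s, one user per arm costs only about four points of power. Large losses need values around 10 SD or more from the mean. The documents give no frequency of use, so the chance of even one such woman is unknown.
- A reader might infer that drug use goes unrecorded. The two histories and the diary could capture it; what the documents support is that no drug record is specified.
- Nothing in the documents shows that anticoagulant, antiplatelet and hemostatic drugs move these four tests to the same degree. The extreme-value calculation fits only drugs that move a test very far.
- Randomization balances use that existed before entry on average, so its main cost is precision. Bias needs unequal use, by chance or after randomization.

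None of this closes the gap. The screening clotting values exist, but no rule uses them for eligibility or adjustment.

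**Conclusion.** The point holds in limited form. Four primary outcomes are open to distortion by drugs that the plan neither screens for nor specifies as data, and the chosen test has no protection against extreme values. The main risk is a missed difference: under the assumptions above, power of about 93% falls to between 89% and 0.4% with one user in each arm, depending on how extreme her PT is. A false difference generally needs about three or more users in the same arm. A reader might go further and infer that the clotting results will be invalid. The documents do not support that, because they give no PT distribution, drug effect or frequency of use. The point deserves action because the change is small and the missing information may not be recoverable later.

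**What to change.** 1. **Eligibility (Section B).** Make current anticoagulant use an exclusion criterion, asked in the screening history. This is for interpretability of the outcome and implies nothing about whether any woman should change a treatment.
2. **Data item (Section C).** At both visits, record by name and date any drug that acts on clotting or is given for the bleeding. Tabulate use by arm.
3. **Analysis (Section D).** Compare each coagulation index in all randomized women, adjusted for the screening value already collected, and repeat with a rank-based test. Adjustment helps where use predates entry; the rank test limits the pull of any extreme value, including one that arises after randomization.
4. **Supportive only.** An analysis that drops women who took such a drug after randomization may be added as a sensitivity analysis. It conditions on something treatment could affect, so its possible bias should be stated.

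The cost is one eligibility sentence, one entry on a history already taken twice, and a few lines in Section D. A few screened women are lost, and the result does not apply to women on anticoagulants.
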